### **3.7.3 Sample Size Calculation for Nurses**

The universal sampling method was used to recruit neonatal nurses in view of the small number of nurses available as the target population for this study. Therefore, all the available nurses i.e 46 nurses and 1 head nurse were invited to participate in the study on a voluntary basis.

### **3.8 Research Instrument**

A questionnaire was the primary analysis instrument for data collection. A questionnaire is a well-established tool for social science research data collection (Dillman & Smyth, 2007). The measurement scale was chosen for this study from the review of the literature and from previous research. For this study, two sets of research tools were used to collect the mothers and nursing outcomes. Questionnaire I [Appendix E(a) & E(b)] was for the mothers and Questionnaire II (Appendix H) was for the nurses. Questionnaire I was provided in two major languages i.e. English and translated Malay version for better understanding for the mothers in Malaysia who is not well versed in English. Questionnaire II was available in

English, while the instrument for the premature infants was the Kangaroo Care Progress Record (KCPR) or booklet with English and Malay versions provided (Appendix I)

### **3.8 Mothers**

#### **3.8.1 Questionnaire I**

This questionnaire contained two sections: Section A, Mother's demographic characteristics and Section B, which consisted of four main parts: Parts I, II, III examined mothers' perception, knowledge, and perceived barriers related to the KC technique and Part IV measured their maternal stress levels when their premature infant was admitted to the NICU.

There were 57 items. [Refer to Appendix E(a) and E(b)].

##### ***Section A: Demographic Characteristics***

Section A collected the demographic characteristics of mothers in the NICU at UMMC. All fourteen (14) variables were designed to gather the baseline data and follow the study's objectives. The variables included in this study were maternal age (years), race, religion, marital status, delivery type: spontaneous vertex delivery (SVD) or caesarean section, parity of mother: primipara or multipara, highest educational level, occupational status, employment sector status, maternity leave status, household income (RM), breastfeeding status, post-partum stress status (pre and post) and KC training course. The rationale for using these data was to assess if the variables chosen had any effect on the perception, knowledge, perceived barriers, and level of stress of the participants.

##### ***Section B: Perception, Knowledge, Perceived Barriers, And Stress.***

###### ***a) Part I: Mother's Perception of Kangaroo Care***

Part I, the mother's perception of KC, was adapted from the original KCQs tool, developed by Arthur J Angler, & Eileen Brumbaugh., Ludington-Hoe et al. (2013). A similar questionnaire was used for the nurses' perception of KC. However, there were differences between nurses and mothers in the items in the informational needs questionnaire; each item

in the mothers' perception section was slightly modified according to the mothers' needs. For the nine (9) items that were modified refer to Appendix B. A 5-point Likert response format was adopted. The descriptor strongly disagree (1) was the lowest scale, followed by disagree (2), neither agree nor disagree (3), agree (4) and strongly agree (5). Out of 20 items there were five items (4,5,8,17,19) that were reversely rated. To identify the level of change in mother's perception regarding the KC technique, the perception scores were transformed into mean scores and then divided into two groups: high perception was below  $M=2.92$  and low perception was above  $M=2.92$ .

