***a) Part I: Nurses' Perception of Kangaroo Care***

Part I assessed nurses' perception of KC related to their personal beliefs and the experiences that they had in the NICU. All twenty-five (25) items were adapted from the original KCQ tool developed by Arthur J. Angler & Eileen Brumbaugh, Ludington-Hoe et al. (2013), with slight modifications to meet the objectives of the study. A 5-point Likert response format was adopted. Descriptors were: strongly disagree (1) as the lowest score, followed by disagree (2), neither agree nor disagree (3), agree (4) and strongly agree (5); descriptor 5 was the highest score. With reference to the descriptors, the closer the score was to 5, the greater the appropriateness of the item. The items were positively and negatively worded (Appendix G). Positive items answered as 'strongly agree' or 'agree' were considered correct and if answered as 'strongly disagree', 'disagree' and 'neither agree nor disagree' were considered incorrect. The negative items were reversely rated. Out of 25 items there were 15 positive statements, which were (1,2,8,9,10,13,15,16,17,18,20,21,22,24,25), and 10 negative

statements, which were (3,4,5,6,7,11,12,14,19,23). The perception scores were converted into mean scores and then categorized into two groups. Mean scores of  $M=2.77$  and below indicated a high perception of KC, while mean scores above  $M=2.77$  indicated a low perception related to KC implementation. Therefore, mean scores of above 2.77 indicated less experience of KC with preterm infants in the NICU.

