***c) Part III: Nurses' Practice of Kangaroo Care***

Part III related to nurses' satisfaction in practicing KC with premature infants with various types of conditions or treatment in the NICU. The eleven (11) items were formulated by adopting the subscale for practices with monitoring devices. The items were adapted from the original KCQ tool developed by Arthur J. Angler & Eileen Brumbaugh, Ludington-Hoe et al. (2013) with minor changes to meet the study objectives and specifications. Nurses were requested to circle a number to indicate their confidence level and skills based on a 5-point Likert scale. The descriptors were: very uncomfortable (1), somewhat uncomfortable (2), neither comfortable (3), somewhat comfortable (4) and very comfortable (5). Out of 11 items, there were four positive statements, which were (1,2,5,6), and seven negative statements, which were (3,4,7,8,9,10,11) Table 3.11. The items were positively and negatively worded. Practice scores for the monitoring device were converted to mean scores and then divided into two categories. Mean scores of  $M= 2.26$  and below indicated a high level of confidence and skills in initiating KC, while mean scores above  $M=2.26$  indicated a low level of confidence and skills in initiating KC with monitoring devices in the NICU.

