### Part I: Mother's Perception of KC

No	Statement	5	4	3	2	1
1	All preterm babies should be allowed to participate in KC regardless of age.					
2	All preterm babies should be allowed to participate in KC regardless of weight.					
3	Babies receiving IV fluids should NOT be allowed to participate in KC.					
4	KC encourages the parenting role.					
5	KC enhances the attachment process between mother and baby.					
6	KC interrupts babies care giving.					
7	KC should be available only to breastfeeding mothers.					
8	KC is NOT feasible with some babies.					
9	KC keeps mothers too tied to the bedside.					
10	KC should be offered to all mothers in the NICU.					
11	KC will benefit preterm babies.					
12	KC will help mothers feel more confident in caring for their preterm babies.					
13	KC will improve the baby's outcome.					
14	KC will interfere with the completion of my tasks.					
15	Learning about KC will help me be a better mother.					
16	Nurses look forward to introducing KC to a new mother.					
17	My babies have adequate time for mother-baby contact without the use of KC.					
18	The increased amount of time required to prepare a baby for a KC session is out of proportion to the benefits.					
19	The teamwork required between nurses and mothers when doing KC is worth the effort.					
20	There is NOT enough flexibility in the NICU to allow mothers extended visits (more than 1 hour) for KC.					

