### Part III : Practice on KC

**Instruction:** Please describe how comfortable are you to initiate KC on baby with the following items? Use the following scale:

5 = Very Comfortable

4 = Somewhat Comfortable

3 = Neither Comfortable Nor Uncomfortable

2 = Somewhat Uncomfortable

1 = Very Uncomfortable

No.	Statement	5	4	3	2	1
1	Baby with intravenous catheters.					
2	Baby during the perioperative period.					
3	Baby with endotracheal intubation.					
4	Baby with high-frequency rate or ventilator mode.					
5	Baby with nasal cannula oxygen (nasal prong).					
6	Baby with Nasal Continuous Positive Airway Pressure (NCPAP).					
7	Baby with percutaneous central lines.					
8	Baby with phototherapy treatment.					
9	Baby with Umbilical Arterial Catheters (UAC).					
10	Baby with Umbilical Venous Catheters (UVC).					
11	Baby with anotrope/vasopressors.					

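### The stated scoring keys and high/low labels contradict the printed questionnaires: the mothers' perception score nets to about zero for an even change in attitude, and nurses who favour kangaroo care are labelled low

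*Combined protocol and SAP*

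**What the plan says.** **Mothers' perception** (Section 3.8.1, Section B, Part I). Responses run from 1 = strongly disagree to 5 = strongly agree. The reversal rule is: "Out of 20 items there were five items (4,5,8,17,19) that were reversely rated". Scores are then "divided into two groups: high perception was below" 2.92, with low perception above it.

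**Nurses' perception** (Section 3.10.1, Part I). Ten of 25 items are called negative and reversed. The text says that "the closer the score was to 5, the greater the appropriateness of the item". Yet a mean of 2.77 "and below indicated a high perception of KC, while mean scores above" 2.77 indicated low perception.

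**Nurses' practice** (Section 3.10.1, Part III; Appendix H, Part III). The form asks: "Please describe how comfortable are you to initiate KC on baby with the following items", with 5 = very comfortable for all 11 items. Section 3.10.1 calls seven of them (3, 4, 7, 8, 9, 10, 11) negative and does not say whether they are reversed. A mean of 2.26 "and below indicated a high level of confidence and skills in initiating KC, while mean scores above" 2.26 indicated a low level.

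**Knowledge** (Sections 3.8.1 and 3.10.1, Part II). Answers are coded 1 = not sure, 2 = false, 3 = true, and are also classed as correct or incorrect. The mothers' positive items are 1, 2, 4, 6, 7, 8 and the negative items 1, 2, 3, 5, 11. The cuts for good knowledge are 2.03 (mothers) and 2.34 (nurses). Section 3.19.4 reports a KR20 of 0.785 for mothers' knowledge and an alpha of 0.813 for mothers' perception.

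**The concern.** A summed attitude scale is interpretable only if every item points the same way after reversal. The stated mothers' key reverses favourable items (item 19 reads "The teamwork required between nurses and mothers when doing KC is worth the effort") and leaves most unfavourable ones alone. The mean then largely measures the tendency to agree with statements.

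Objectives 1 and 3 are tested on these mean scores with the general linear model and repeated measures (Table 3.4). If the written key was run, a real and even gain in mothers' perception would give no expected change, and a gain confined to the unfavourable items would look like a decline. The inverted labels would report nurses who favour KC as having low perception. Weight gain, length of stay and breastfeeding do not use these scales.

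**Working it through.** **Mothers' perception.** The plan reverses five items. Appendix E(a) has nine unfavourably worded items (3, 6, 7, 8, 9, 14, 17, 18, 20), and only two of those (8, 17) are on the list.

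- Rising with a favourable attitude: 8 favourable unreversed (1, 2, 10, 11, 12, 13, 15, 16) + 2 unfavourable reversed (8, 17) = 10.
- Falling: 3 favourable reversed (4, 5, 19) + 7 unfavourable unreversed (3, 6, 7, 9, 14, 18, 20) = 10.

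The nurses' key treats the parallels of mothers' items 8, 17 and 20 (nurses' 13, 22, 25) as positive. On that coding 9 items rise and 11 fall. Shift in the mean = (rising - falling)/20 for a 1-point improvement:

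| Improvement on | Stated key, by wording | Consistent key | Stated key, nurses' coding | Consistent key |
|---|---|---|---|---|
| all items | (10-10)/20 = 0.00 | +1.00 | (9-11)/20 = -0.10 | +1.00 |
| favourable items only | (8-3)/20 = +0.25 | 11/20 = +0.55 | (9-5)/20 = +0.20 | 14/20 = +0.70 |
| unfavourable items only | (2-7)/20 = -0.25 | 9/20 = +0.45 | (0-6)/20 = -0.30 | 6/20 = +0.30 |

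By wording, fully favourable and fully unfavourable mothers both score 3.00, which is above 2.92 and so low. On the nurses' coding they score (9×5+11×1)/20 = 2.80 and (9×1+11×5)/20 = 3.20. Agreeing with every item gives (15×5+5×1)/20 = 4.0; disagreeing with every item gives (15×1+5×5)/20 = 2.0. Treating the arguable items 8, 16 and 20 as neutral, in any combination, keeps the net between -0.10 and +0.05.

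**Does the reported alpha fit?** Assume equal inter-item correlations r and correct keying. Then 0.813 requires r = 0.813/(20-19×0.813) = 0.179. Under the 10/10 key the mean correlation is (90-100)/190×0.179 = -0.0094, so alpha = 20×(-0.0094)/(1-19×0.0094) = -0.23. Under 9/11 it is -0.18. Neither is near 0.813.

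**Nurses' perception.** By wording, the stated key leaves 22 items favourable and 3 (13, 22, 25) not. Fully favourable: (22×5+3×1)/25 = 4.52, or 5.00 if the plan's own coding is accepted. Both exceed 2.77, so low. Fully unfavourable: (22×1+3×5)/25 = 1.48, or 1.00. Both are called high.

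**Practice.** Fully comfortable: 5.00 with no reversal, (4×5+7×1)/11 = 27/11 = 2.45 with seven reversed. Both exceed 2.26, so low. Fully uncomfortable: 1.00 (high) or (4×1+7×5)/11 = 39/11 = 3.55 (low).

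**Knowledge.**
- Mothers' items 1 and 2 are in both lists and 9 and 10 in neither. Only 3, 4, 5, 6, 7, 8 and 11 (7 of 11) have one key.
- Mothers' items 6 and 8 contradict each other (one calls KC contraindicated in premature infants, the other calls it safe for them), yet both are keyed positive.
- Mothers' item 5, on breathing patterns, is keyed negative; its nurses' parallel (item 7) is keyed positive.
- Correct/incorrect scoring and KR20 imply 0/1 items, but cuts of 2.03 and 2.34 cannot occur on a 0/1 mean.
- If the nurses' negative items are reversed on the 1/2/3 codes, all correct gives (33+18)/20 = 2.55, while answering not sure to all nine negatives gives (33+27)/20 = 3.00.

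**Minor.** Barrier items 16 and 17 are worded as barriers but reversed, so the range is (17×1+2×5)/19 = 1.42 to (17×5+2×1)/19 = 4.58 instead of 1 to 5. On the Malay stress scale (Appendix E(b), Bahagian IV), codes 5 and 4 carry the same label.

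**The case against.** The strongest reply is that the printed key was probably not the one run. The alpha result points that way. So does the mothers' negative knowledge list (1, 2, 3, 5, 11), which is identical to the first five entries of the nurses' list and looks like a copying slip. This stands: the text certainly contradicts the forms, but the shifts above apply only if the written key was executed.

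Other points have some force:

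- Inverted labels do not alter mean-based tests. They affect descriptive statements and any chi-square tables built on the categories. Only the key errors change means.
- Section 3.8.1 refers to Appendix B and Tables 3.3 and 3.4 for item wording, and Section 3.10.1 to Table 3.11. Tables 3.3 and 3.4 as printed are the nurses' schedule and the analysis summary, and no Table 3.11 appears. Unseen material might explain the numbering, but it cannot reconcile the key with the printed forms.
- Malay item 19 says teamwork is needed, which is less clearly favourable than the English. Treating it as neutral moves the net only to (10-9)/20 = +0.05.
- On a natural reading, reversing a knowledge item just means that false is the correct answer. The 2.55 against 3.00 contrast therefore illustrates an ambiguity and is not a demonstrated result.
- The nurses' knowledge key is no gold standard. It keys item 1 (infants seem content in KC) as negative. The item 5/item 7 mismatch shows inconsistency between forms, not which form is right.
- The barrier items and the Malay label would not justify a mandatory correction alone.

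**Conclusion.** The point holds and needs correcting before the questionnaire results are relied on. As written, the mothers' perception mean responds to an even 1-point improvement by 0.00 (-0.10 under the nurses' coding, +0.05 at most under the other readings tried) instead of +1.00. The nurses' perception labels are the reverse of the stated score direction. A fully comfortable nurse is called low on practice whether or not the seven items are reversed. The mothers' knowledge score cannot be reproduced from the stated lists.

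The zero assumes an even change across items; an uneven change moves the mean, but not in an interpretable direction. The alpha comparison assumes equal inter-item correlations. Item direction was judged from the printed wording, and the executed SPSS syntax is not shown. If the syntax matched the text, the mothers' perception result is uninterpretable. If it did not, the plan misstates how an objective-level outcome was scored. Either case needs the same correction.

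**What to change.** 1. Retrieve the scoring syntax actually used and compare it with the tool developers' key.
2. Publish one item-level key per scale that matches the printed forms. By wording, and subject to the developers' key: for mothers' perception, reverse 3, 6, 7, 9, 14 and 18, and do not reverse 4, 5 or 19. Settle mothers' 8, 17 and 20 and nurses' 13, 22 and 25 the same way on both forms; their wording points to reversal. Check item 19 against the Malay version. Reverse no practice or barrier items.
3. Score both knowledge scales as correct = 1, otherwise 0, with one keyed answer for every item, and reconcile mothers' items 6 and 8.
4. Define high perception and high practice as at or above the cut. Recompute the cuts and the pilot reliability coefficients.
5. Rescore the item-level data before running the general linear model and repeated-measures analyses.
6. Report the duplicated Malay stress label as a limitation; completed forms cannot be repaired.

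The cost is a syntax check, one scoring table and a re-run on existing data. No new data collection is needed.

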***b) Part II: Mother's Knowledge on Kangaroo Care***

Part II of the mother's knowledge questionnaire was adapted from the original KCQs tool developed by Arthur J. Angler, & Eileen Brumbaugh, Ludington-Hoe, et al. (2013) with slight modifications so as to be relevant and meet the objectives of the mothers' outcomes. There were similar knowledge questionnaires for the mothers and nurses regarding their ability to implement KC. Mothers were requested to circle a number and indicate their opinion on their knowledge of KC. The scoring was from not sure (1) to false (2) and true (3). The items were worded in both positive and negative terms (Table 3.3). Positive items answered with 'true' were considered correct and incorrect if they were answered 'false' or 'not sure'. Out of 11 items, there were six positive statements, which were (1,2,4,6,7,8), and five negative statements, which were (1,2,3,5,11). A higher score indicated a higher level of knowledge with reference to the descriptors. Higher mean scores of  $M=2.03$  and above-indicated mothers had a good level of knowledge regarding KC, while lower mean scores below  $M=2.03$  indicated a poor level of knowledge on KC.

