***b) Part II: Nurses' Knowledge of Kangaroo care***

The Part II questionnaire was on nurses' knowledge, determined by 20 true-false items to assess nurses' knowledge pertaining to initiation of KC with preterm infants in the NICU setting. The items were adopted from the KCQ tool developed by Arthur J. Angler & Eileen Brumbaugh, Ludington-Hoe et al. (2013). Nurses had to grade their level of knowledge according to 'not sure' (1), 'false' (2) and 'true' (3). These items were selected because they contained sufficient information to evaluate or report on the KC-related knowledge of mothers and infants. The items were worded in a positive and negative way. Positive items answered as 'true' were considered correct and if answered 'false' or 'don't know' were considered incorrect. The negative items were reversely rated. Out of 20 items there were 11 positive statements, which were (4,6,7,8,9,10,13,14,15,18,19), and nine negative statements, which were (1,2,3,5,11,12,16,17,20). The scores for knowledge were converted into mean scores, and then classified into two parts. Higher mean scores of  $M=2.34$  and above indicated good knowledge, while mean scores below  $M=2.34$  indicated poor knowledge and experiences in relation to KC in the NICU.

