## Part II: Knowledge on KC

**Instruction:** Please answer the following questions to the best of your ability based on your own personal knowledge of KC, **NOT** on its practice. Circle your response that best represents to knowledge of KC. Use the following scale for your responses:

3 = True

2 = False

1 = Don't know

No	Statement	True	False	Not sure
1	Babies appear to be satisfied in KC.	3	2	1
2	Babies on phototherapy can participate in KC.	3	2	1
3	Babies typically decrease heart rate during KC.	3	2	1
4	Babies with peripheral IVs can participate in KC.	3	2	1
5	KC has been shown to improve breathing patterns in preterm babies.	3	2	1
6	KC is contraindicated in premature babies.	3	2	1
7	KC is contraindicated in babies weighing less than 1000 grams.	3	2	1
8	KC is now considered safe as an alternative approach to care for preterm babies.	3	2	1
9	Most babies experience a decrease in temperature during KC.	3	2	1
10	KC increase risk of infection in premature babies.	3	2	1
11	KC cause more stress with heart problem babies.	3	2	1

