## Bahagian II : Pengetahuan terhadap KC

**Arahan** : Sila jawab soalan-soalan berikut dengan tepat mengikut kemampuan anda berdasarkan pengetahuan peribadi anda sendiri mengenai KC, **TIDAK** pada amalannya. Bulatkan jawapan yang terbaik untuk mewakili pengetahuan KC anda. Gunakan skala berikut untuk jawapan anda:

3 = Benar

2 = Salah

1 = Tidak pasti

No	Statemen	Betul	Salah	Tidak Pasti
1	Bayi kelihatan berpuas hati dengan KC.	3	2	1
2	Bayi dengan rawatan fototerapi boleh mengambil bahagian dalam KC.	3	2	1
3	Bayi biasanya mengurangkan kadar jantung ketika KC.	3	2	1
4	Bayi dengan Intra periferal boleh mengambil bahagian dalam KC.	3	2	1
5	KC telah membuktikan dapat membantu kadar pernafasan pada bayi pramatang.	3	2	1
6	KC tidak sesuai pada bayi pramatang.	3	2	1
7	KC tidak sesuai pada bayi yang berat kurang daripada 1000 gram.	3	2	1
8	KC kini dianggap selamat sebagai pendekatan alternatif untuk menjaga bayi pramatang.	3	2	1
9	Kebanyakan bayi mengalami penurunan suhu semasa KC.	3	2	1
10	KC adalah peningkatan risiko jangkitan pada bayi pramatang.	3	2	1
11	KC tidak sesuai untuk bayi yang mempunyai masalah jantung.	3	2	1

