## Indication infants for Kangaroo Care(Cont.)

- Incubator / open air crib - can maintain (36.8 – 37.4 °C)
- Stable in low rate ventilator
- Dosages of medications have stabilized
- No O2 supplement or with low O2
- Consistently taking milk well.
- Gain weight (15 – 20 grams/day for 3 - 5 days/ 10 – 15 gram/day)
- Infant with phototherapy – Mother presses the fiber - optic blankets against the infant's back while doing KC.

22

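### The mothers' knowledge key lists items 1 and 2 in both directions, omits items 9 and 10, and credits the belief that premature babies should not have KC

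*Combined protocol and SAP*

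**What the plan says.** Section 3.8.1, part b (mothers' knowledge), gives the response codes: "The scoring was from not sure (1) to false (2) and true (3". It then gives a right/wrong rule: "Positive items answered with 'true' were considered correct and incorrect if they were answered 'false' or 'not sure". It assigns the items as follows: "there were six positive statements, which were (1,2,4,6,7,8), and five negative statements, which were (1,2,3,5,11". It gives no scoring rule for the negative items. A mean of 2.03 separates good from poor knowledge.

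The items themselves are in Appendix E(a), Part II. Item 6 is "KC is contraindicated in premature babies"; the Malay form in Appendix E(b) has the same meaning, "KC tidak sesuai pada bayi pramatang". Item 5 is "KC has been shown to improve breathing patterns in preterm babies". Items 9 and 10 say that temperature usually falls during KC and that KC raises infection risk.

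The nurses' form is keyed separately in Section 3.10.1, part b, with 11 positive items and "nine negative statements, which were (1,2,3,5,11,12,16,17,20". There the negative items are explicitly reverse-rated.

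**The concern.** Mothers' knowledge is a named outcome of specific objective 1 and of H1. The score can measure learning only if the answer keyed correct is the one the programme teaches. The theory module in Section 3.11 presents KC as a way of caring for premature infants and tells mothers that it steadies temperature, heart rate and breathing and lowers infection. A key that marks 'true' correct on item 6 contradicts that premise. A key that lists two items in both directions and omits two others cannot be applied as printed. On the affected items, a mother who learns the material may gain nothing, or may score below one who believes the reverse.

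**Working it through.** **Step 1: the lists as sets.** Positive = {1, 2, 4, 6, 7, 8}; negative = {1, 2, 3, 5, 11}. Entries: 6 + 5 = 11, which matches the stated item count. Distinct items: 11 − 2 = 9. In both lists: {1, 2}. In neither: {9, 10}. Keyed once: {3, 4, 5, 6, 7, 8, 11}, seven items. So the stated split of 11 items into six and five is not reproduced by the lists. The nurses' lists do not have this fault: 11 + 9 = 20, each item once.

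**Step 2: where the numbers may come from.** The nurses' negative items numbered 11 or lower are {1, 2, 3, 5, 11}, identical to the mothers' negative list. The two forms number their statements differently (wording paraphrased):

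| Statement | Mothers' item: key | Nurses' item: key |
|---|---|---|
| Babies seem content in KC | 1: both | 1: negative |
| Baby under phototherapy may have KC | 2: both | 3: negative |
| Baby with a peripheral line may have KC | 4: positive | 6: positive |
| KC helps breathing | 5: negative | 7: positive |
| KC unsuitable below 1000 g | 7: positive | 9: positive |
| KC a safe alternative | 8: positive | 10: positive |
| Temperature falls | 9: none | 11: negative |
| Infection risk rises | 10: none | 17: negative |

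Nurses' item 6 (peripheral line) fits positive keying; mothers' item 6 is a different statement. Nurses' item 5 is about more bradycardia; mothers' item 5 is about better breathing. This suggests that item numbers were carried from one form to the other.

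**Step 3: score a mother who answers as taught.** Take the seven items whose answer the programme or procedure text supports: 1, 4, 5 and 8 'true'; 6, 9 and 10 'false'. Score positive items correct if 'true' and, borrowing the nurses' rule, negative items correct if 'false'.

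- Printed key: marks on 4 and 8; zero on 5 and 6; conflict on 1; no key for 9 and 10. Total 2. Answering 'true' throughout earns 3 (items 4, 6 and 8).
- Replace 1, 2 by 9, 10 in the negative list, giving {3, 5, 9, 10, 11}: all 11 items are covered once, but the taught answers score only 5 of 7, with 5 and 6 still marked wrong.
- Also move 5 to positive and 6 to negative: 7 of 7.

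**Step 4: the raw codes, unreversed.** The taught pattern averages (4 × 3 + 3 × 2)/7 = 18/7 = 2.57; 'true' throughout averages 21/7 = 3.00.

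**Step 5: what learning does on item 6.** Under the right/wrong rule, 'true' to 'false' goes from 1 to 0, and 'not sure' to 'false' stays at 0. Under the raw codes, 'true' to 'false' goes from 3 to 2, and 'not sure' to 'false' goes from 1 to 2.

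**The case against.** The strongest reply is that 1, 2 in the negative list is a slip for 9, 10. The complement of the six positive items is exactly five items, three of which are already printed as negative. Section 3.8.1 also points to Table 3.3 for item direction, whereas Table 3.3 in this document is the nurses' schedule, so the key actually used may lie elsewhere. This is plausible and would resolve the overlap and the omission. It would not resolve item 6, nor item 5 if negative items are reversed.

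The reply also limits what can be claimed:

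- Item 5 depends on reverse rating, which the mothers' knowledge section does not state. Item 6 needs no such assumption.
- A reader might infer that mothers who learn will lose marks overall. The documents do not support that: on item 6 only a move from 'true' costs a mark, and items 4 and 8 still reward learning.
- A reader might convert the faults into ceilings, such as 7 of 9 for mothers or 17 of 20 for nurses. Those are right/wrong totals. The cut-offs, 2.03 and 2.34, are means on the 1–3 codes, and Table 3.4 refers to mean scores. KR20 in Section 3.19.4 suggests right/wrong scoring in the pilot, but nothing says that a right/wrong total is the trial outcome.
- A reader might extend the fault across the nurses' key. That key is complete. Item 20 (ventilated babies do well) is not contradicted by a slide that merely lists stability on a low ventilator rate as an indication, and the case on item 1 is an inference from a slide about the amygdala and contentedness.
- Weight gain and length of stay are the named primary outcomes; knowledge is not.

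**Conclusion.** The mothers' knowledge key is wrong as written. Four of 11 items (1, 2, 9, 10) have no usable key as printed. Of the other seven, item 6 is keyed against the programme under the plan's own explicit rule. Item 5 is too, and against the nurses' key for a near-identical statement, on the assumption that negative items are reverse-rated for mothers as they are for nurses.

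These items withhold or reverse credit for learning in a stated H1 outcome. It is tempting to say that the group difference is therefore pulled toward zero. The documents do not establish this: size and net direction depend on how many mothers start at 'true', 'false' and 'not sure', and on whether keyed marks or raw codes are analysed. Neither is given. If the printed list is only a reporting error, the key actually used still has to be stated.

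**What to change.** Replace the two lists in Section 3.8.1, part b, with one key for items 1 to 11 set from the mothers' wording in Appendix E:

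- Put each item in one list only: items 1 and 5 positive; items 6, 9 and 10 negative, in line with the Section 3.11 module.
- State that negative items are reverse-rated, and say which score enters the analysis.
- For items that turn on a clinical eligibility rule (mothers' items 2 and 7, nurses' item 3), reconcile key, course slides and exclusion criteria before scoring, or leave the items out. On phototherapy, Appendix P lists under indications "Infant with phototherapy – Mother presses the fiber - optic blankets against the infant's back while doing KC", while the nurses' key makes that item negative and Sections 3.7.1 and 3.16.4 exclude some infants who need phototherapy. On weight, the mothers' key agrees with the Appendix P contraindication slide (1000 g), but the sitting-transfer slides use 1500 g.
- Check nurses' item 1 against the course content, since the same statement is mothers' item 1 and the two keys should agree.
- Re-score every visit in both groups from the stored item answers.

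The cost is one key table and a re-run of the scoring, with slightly shorter scales if unresolved items are dropped.
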